#### **Control treatment**

Intravenous prophylaxis with 0.9% NaCl before and after contrast exposure (n=133). It will consist of in-hospital administration of 3 mL/kg in the hour before and 2 mL/kg in the 4 hours after the procedure. The NaCl solution used as a control drug is commercialized in our country and will be acquired by the promoter through the Hospital Pharmacy department, which will be responsible for its labeling and distribution.

#### **Contrast used**

The contrast used will be iodixanol (320 mg iodine/mL). A volume of 100 mL, at infusion rate 2-5 mL/s will be administered.

### **5.6. Schedule**

Estimated duration of the clinical trial is 3 years.

#### **Trial schedule**

- Preparation of the study (3 months): Planning work for adequate information to patients, acquire the necessary material and schedule the laboratory determinations and the application of protocols.
- Development of the study: progressive inclusion and follow-up of patients, as well as sample collection (estimated at 8 patients per month). It is estimated that 30 months will be needed to include the 266 patients. This phase could be prolonged due to limitations in the recruitment. The protocol for the collection of samples will be applied to process and conserve the samples.
- Determinations of serum and urinary markers will be performed at the same time in an estimated period of 3 months. NAG, NGAL, KIM-1, GM2AP, t-gelsolin will be measured.
- Elaboration of the database for the inclusion of clinical and analytical variables. Collection and computerization of clinical data and analytical results (6 months).
- Statistical study of the results and their interpretation. Writing of the work and publications (5 months).

### **5.7. Completion criteria**

Patients will terminate their participation in the study for the following reasons:

- Completion of treatment according to the study protocol.
- Medical safety reasons, at the discretion of the responsible Investigator.
- Serious adverse effect or adverse effect that the Researcher considers unacceptable.
- Voluntary abandonment by the patient.
- Death.
- Demonstration during follow-up that the patient did not meet the criteria for inclusion in the clinical trial.

### **5.8. Study medication accounting**

Study medication should be used in accordance with the study protocol. The Principal Investigator, or the person he/she delegates, will be responsible for administering the study medication. The Principal Investigator will record used and unused medication for each trial patient on a Medication Record Sheet. This Record Sheet will be available for monitoring visits. To ensure traceability of intravenous NaCl the

following will be noted: trade name, quantity and lot number dispensed at each visit. This information will also appear in the electronic data capture system.

In the case of common salt (capsules), a record will be kept of those given to the patient and of the blisters returned by the patient at the 24h visit after the procedure. Accordingly, patient's adherence to the treatment will be assessed.

## **5.9. Randomization**

The Clinical Biostatistics Unit of Hospital Universitario Ramon y Cajal will generate (by computer) a randomization list to assign each treatment. The ratio will be 1:1. This list will be sent to the Pharmacy Department of the hospital, which will be responsible for supplying the study researchers with the treatment corresponding to the patient number in the trial.

## **5.10. Data source**

All procedures and variables related to this work will be collected in an electronic data capture system (EDC). There will be an EDC for each subject included, independently of the group he/she belongs, and all the variables related to the study will be recorded in this EDC. During the study, no personal data will be collected from patients as study participants that would allow identification of the subject. The data obtained will be kept under strict confidentiality (Organic Law 15/1999, on personal data protection) and only the research team of the project will have access to them. Radiological images and other complementary tests related to the study, as well as the EDC will be numbered with a code to guarantee the confidentiality of the sample and the data. During the study period EDC will be kept under lock, which will be held exclusively by the researcher responsible for the project. The coordinators of this study are committed to maintain absolute confidentiality and to protect the information provided to them.

All the information contained in the Clinical History and certified copies of the tests performed, necessary for the evaluation of the clinical trial.

Original documents, data and tests (e.g., medical history, medical charts, nursing charts, pharmacy records, laboratory tests, or radiological studies).

## **5.11. End of clinical trial**

The end of the clinical trial will be the last visit of the last subject enrolled in the study.

# **6. SELECTION AND WITHDRAWAL OF SUBJECTS**

## **6.1. Inclusion criteria**

Patients are eligible to be included if they meet the following inclusion criteria: outpatients, aged over 65 years old, undergoing a contrast-enhanced CT scan, who are at high risk of developing PC-AKI, defined as having at least one of the following risk factors: diabetes mellitus, stable heart failure, chronic kidney disease (MDRD-4 between 30 and 59 mL/min), and capable of giving signed informed consent.

## **6.2. Exclusion criteria**

- Glomerular filtration rate less than 30 mL/min.
- Presence of hypokalemia (serum potassium less than 3.5 mEq/L).
- Performance of other procedures with intravenous contrast in the previous fifteen days.
- Administration of nephrotoxic drugs (NSAIDs, aminoglycosides and/or potentially nephrotoxic chemotherapy) in the last 72 hours, or anticipation of receiving them in the following hours.
- Chronic decompensated pathology: acute heart failure, decompensated COPD or poorly controlled arterial hypertension.
- Allergy to iodinated contrasts.
- Patients diagnosed with hyperchloraemia or hypernatremia.
- When assessing the inclusion of a patient in the study, all the specifications of the technical data sheet in relation to "special warnings and precautions for use" will be taken into account.

## **6.3. Sample size and justification**

The study will be conducted in 266 individuals on an outpatient basis. Taking into account the non-inferiority design, for the determination of the sample size it has been considered acceptable to establish a priori a difference of no more than 5% in the incidence of PC-AKI of oral prophylaxis with respect to intravenous. Considering our high-risk population, we estimated an incidence of PC-AKI in the intravenous group of 7% and 12% in the oral group. With this expected response, a non-inferiority margin of 5%, a power of 80% and a degree of significance of 2.5%, the sample size will be 266 patients, 133 per group.

## **6.4. Withdrawal criteria and analysis**

The patient may discontinue participation in the study at any time he/she wishes. The investigator/physician may also decide to withdraw a patient from the trial if the patient does not meet the protocol standards. Patients will terminate their participation in the study for the following reasons:

- Completion of treatment according to the study protocol.
- Medical safety reasons.
- Serious adverse effect or adverse effect that the Investigator considers unacceptable.
- Voluntary withdrawal by the patient.
- Death.
- Acknowledgement during the follow-up that the patient did not meet the selection criteria for the clinical trial.

## **6.5. Estimated duration of the recruitment period**

The recruitment period is estimated to extend over 30 months.

# **7. DESCRIPTION OF TREATMENT**

## 7.1. Treatment definition

### Treatment A:

Sodium chloride, capsules of 500 mg.

- Dose per subject: 100 mg/kg total administered in several daily intakes during the 48 hours prior to the procedure and 12 hours after.
- Route of administration: oral.

### Treatment B:

Sodium chloride, 0.9%.

- Dose per subject: 3 mL/kg of 0.9% sodium chloride in the hour before and 2 mL/kg in the 4 hours after the procedure.
- Route of administration: intravenous.

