### Experimental and control group

Experimental group: 500 mg capsules of sodium chloride (NaCl), supplied by the Pharmacy Department of the Hospital Universitario Ramón y Cajal. The total dose administered will be 100 mg/kg of body weight distributed in 60 hours, 48 hours before and 12 hours after the procedure. Appendix C describes the specific regimen according to weight.

Control group: 0.9% NaCl solution, supplied by the Pharmacy Department of the Hospital Universitario Ramón y Cajal. Dose: 3 ml/kg in the hour prior to the procedure and 2 ml/kg/hour in the following 4 hours.

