#### **4.2. Benefits and risks for humans**

The intended benefit is the demonstration that oral NaCl is non-inferior to an intravenous administration. This would allow the widespread application of a preventive treatment for contrast nephropathy, easy to administer to all patients. Likewise, the study could help us to identify patients at risk of PC-AKI analyzing the molecules mentioned.

The administration of saline compounds can increase blood volume and increase congestive symptoms such as edema. However, at the doses used and taking into account the criteria required for participation, patients are not expected to suffer any complication from the study. In any case, oral treatment, which is the subject of the study, should not produce more volume overload at the proposed doses than conventional intravenous treatment.

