#### **4.3. Justification of the route of administration, dose, regimen and treatment period**

The proposed intravenous regimen of 11 mL/kg body weight of 0.9% NaCl, over the course of 6 hours is within the accepted recommendations. The oral regimen is intended to provide volume support with NaCl for a reasonable period of 60 hours.

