##### **Control group**

Sodium chloride solution 0.9% will be supplied by the Pharmacy Department of the hospital at a dose of 3 mL/kg in the hour before to the procedure and 2 mL/kg/hour in the 4 hours after.

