### **5.3. Study design**

PNIC-Na is a phase 2, monocenter, randomized, open-label, non-inferiority trial. Two types of preventive treatment will be compared in patients undergoing a CE-CT scan:

- Oral prophylaxis with NaCl capsules and free water intake (250 mL of water with each capsule, ensuring a water intake of 750 mL/day) in the 48 hours prior to contrast exposure (n=133). It will be performed on an outpatient basis at a dose of 100 mg/kg body weight distributed in 60 hours, 48 hours prior to the procedure and 12 hours after. Appendix C describes the specific dose according to weight.
- Intravenous prophylaxis with 0.9% NaCl before and after contrast exposure (n=133). It will consist of in-hospital administration of 3 mL/kg in the hour before and 2 mL/kg in the 4 hours after the procedure.

The contrast used will be iodixanol (320 mg iodine/mL, infusion rate 2-5 mL/sec).

The corresponding treatment will be administered after medical prescription, validation by the pharmacist and confirmation. The nurse in charge of the patient will administer the treatment. The intravenous prophylaxis schedule for the study will begin in the Radiology Department of the Hospital, and will conclude in the Clinical Trials Unit of the same center.

The study will consist on the schedule of visits described in section 9.2.

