**PNIC-Na Protocol**

Date & Version No: 02-Aug-2013 V2.0 (ENG)

80 - <85	880 mL	8 g (16 capsules)
136 mEq	1 hour pre-test 240 mL 0-4 hours post-test 640 mL	48 hours pre-test 2 capsules 40 hours pre-test 2 capsules 32 hours pre-test 2 capsules 24 hours pre-test 2 capsules 16 hours pre-test 2 capsules 8 hours pre-test 2 capsules 0 hours 2 capsules 12 hours post-test 2 capsules
85 - <90	935 mL	8.5 g (17 capsules)
144,5 mEq	1 hour pre-test 255 mL 0-4 hours post-test 680 mL	48 hours pre-test 2 capsules 40 hours pre-test 2 capsules 32 hours pre-test 2 capsules 24 hours pre-test 2 capsules 16 hours pre-test 2 capsules 8 hours pre-test 3 capsules 0 hours 2 capsules 12 hours post-test 2 capsules
90 - <95	990 mL	9 g (18 capsules)
153 mEq	1 hour pre-test 270 mL 0-4 hours post-test 720 mL	48 hours pre-test 2 capsules 40 hours pre-test 2 capsules 32 hours pre-test 2 capsules 24 hours pre-test 2 capsules 16 hours pre-test 2 capsules 8 hours pre-test 3 capsules 0 hours 3 capsules 12 hours post-test 2 capsules
95 - <100	1045 mL	9.5 g (19 capsules)
161,5 mEq	1 hour pre-test 285 mL	48 hours pre-test 2 capsules

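### The intravenous control volume is given two ways: sections 5.3, 5.5 and 7.1 add up to 5 mL/kg, while the Summary, 4.3, 4.5 and Appendix C give 11 mL/kg

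*Combined protocol and SAP*

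**What the plan says.** The intravenous regimen appears in seven places.

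- Section 7.1, Treatment B, the formal dose per subject: "3 mL/kg of 0.9% sodium chloride in the hour before and 2 mL/kg in the 4 hours after the procedure".
- Section 5.3, Study design: "in-hospital administration of 3 mL/kg in the hour before and 2 mL/kg in the 4 hours after the procedure".
- Section 5.5, Control treatment: "3 mL/kg in the hour before and 2 mL/kg in the 4 hours after the procedure".
- Summary, Experimental and control group: "3 ml/kg in the hour prior to the procedure and 2 ml/kg/hour in the following 4 hours".
- Section 4.5, Control group: "3 mL/kg in the hour before to the procedure and 2 mL/kg/hour in the 4 hours after".
- Section 4.3: "The proposed intravenous regimen of 11 mL/kg body weight of 0.9% NaCl", to be given over 6 hours.
- Appendix C, which has an intravenous column in millilitres for every weight band. The 80 to <85 kg row reads "1 hour pre-test 240 mL 0-4 hours post-test 640 mL".

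The Summary and sections 5.3 and 5.5 refer to Appendix C only where they describe the oral arm. The control-arm text in 5.5 and 7.1 does not refer to it. Section 5.3 requires a prescription and validation by the pharmacist, but does not say which text these are checked against. Section 10.6 makes the per-protocol analysis the main one.

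**The concern.** The first three places give the post-procedure amount as a total for the 4 hours. The Summary and 4.5 give the same number as a rate per hour. This is a contradiction within the protocol, and the point is not a criticism of either regimen.

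Three things depend on it:

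- **The comparator.** A non-inferiority result can be interpreted only if the active control was given as intended. Staff who follow 7.1 as written would give less than half the Appendix C volume across the closed weight bands. The protocol's rationale is that hydration protects the kidney, so that would be a materially different control.
- **Per-protocol status.** With two volumes in the protocol, the same infusion can be called compliant under one section and a deviation under another.
- **The risk statement.** Section 4.2 says that oral treatment "should not produce more volume overload at the proposed doses than conventional intravenous treatment". If the trial's own control is the reference, the salt loads behind that statement differ widely between the two readings.

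A lesser inconsistency affects the oral arm. Sections 5.3 and 5.5 tie 250 mL of water to each capsule, whereas 4.5 and Appendix C tie it to each oral dose.

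**Working it through.** **1. Total volume per kg.** Total = amount before + amount after.

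| Source | Before | After | Total |
|---|---|---|---|
| Summary, 4.5 | 3 mL/kg | 2 mL/kg/hour × 4 h = 8 mL/kg | 11 mL/kg |
| 4.3 | not split | not split | 11 mL/kg (stated) |
| Appendix C, lower weight limit | 3 mL/kg | 8 mL/kg | 11 mL/kg |
| 5.3, 5.5, 7.1 | 3 mL/kg | 2 mL/kg | 5 mL/kg (sum; not printed) |

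The hourly wording therefore reproduces the total in 4.3, and the wording of 5.3, 5.5 and 7.1 does not.

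**2. Appendix C.** In all 11 rows the two volumes add up to the row total, and dividing by the lower weight limit gives 3 + 8 = 11 mL/kg. Examples: 150 + 400 = 550 mL at 50 kg; 240 + 640 = 880 mL at 80 kg; 300 + 800 = 1100 mL at 100 kg. The volumes are fixed within a band, so at the upper limits of the closed bands the figure falls to between 550/55 = 10.0 and 1045/100 = 10.45 mL/kg. None of these is near 5.

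**3. Size at 80 kg.** 5 × 80 = 400 mL against 11 × 80 = 880 mL. The ratio is 880/400 = 2.2, and the shortfall is 480/880 = 55%. After the procedure it is 2 × 80 = 160 mL against 640 mL, a four-fold difference. Across the bands, at the lower weight limits, the totals are 250 to 500 mL against 550 to 1100 mL.

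**4. Salt load.** A 0.9% solution contains 9 mg/mL.

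- At 5 mL/kg: 5 × 9 = 45 mg/kg; oral to intravenous = 100/45 = 2.22.
- At 11 mL/kg: 11 × 9 = 99 mg/kg; oral to intravenous = 100/99 = 1.01.

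**5. The sodium totals in Appendix C.** Each row carries one mEq figure for both arms. Taking 58.44 mg of NaCl per mEq, the 80 kg row works out as follows:

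- 880 mL: 7920/58.44 = 135.5 mEq.
- 16 capsules: 8000/58.44 = 136.9 mEq.
- Printed figure: 136 mEq.
- 400 mL: 3600/58.44 = 61.6 mEq.

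In the ten rows from 50 to <100 kg the printed figure is within 1% of both arms' Appendix C amounts. The >100 kg row prints 177 mEq, which matches neither 1100 mL (9900/58.44 = 169.4) nor 10 g (10000/58.44 = 171.1).

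**6. Water in the oral arm (lesser point).** From 48 hours before the test through the 0-hour dose there are 7 doses, and 9 capsules (lightest band) to 18 capsules (heaviest). Per dose this is 7 × 250 mL = 1.75 L; per capsule it is 2.25 to 4.5 L. Counting only the doses at 48 to 8 hours before, 6 doses give 1.5 L, and 7 to 15 capsules give 1.75 to 3.75 L.

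**The case against.** The strongest reply is that this is one drafting slip repeated. The two wordings differ essentially by a time unit, no section prints a total of 5 mL/kg, and Appendix C is the only place that gives the infusion in millilitres. Staff who work from that table would not meet the conflict. That lowers the chance of a dosing error, and no error has been shown. It does not remove the contradiction: one version stands in three sections, including the formal treatment definition, and no text makes the table controlling for the intravenous arm.

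Some narrower objections stand as qualifications:

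- The >100 kg row is fixed at 1100 mL. At 5 mL/kg a 110 kg patient would receive 550 mL, exactly half, and a 120 kg patient 600 mL, or 55%. The phrase less than half therefore fails from 110 kg upward.
- Section 4.2 compares oral treatment with conventional intravenous treatment, not expressly with the trial's control. The 2.2 ratio is one of salt load, and oral dosing is spread over 60 hours. It does not measure volume overload.
- The protocol sets no volume criterion for per-protocol status in the intravenous arm, and 7.2 describes adherence assessment only for capsules. The missing definition of the per-protocol population is a separate issue. The conflict here would remain even with such a definition, because the definition would have to choose one volume.
- On water, three 8-hourly doses of 250 mL make the 750 mL per day that all four places give, and 7.1 allows free water. This softens the point, but the two instructions still differ.

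**Conclusion.** The concern holds. The protocol contradicts itself on the volume given to its active control: 5 or 11 mL/kg in total, a 2.2-fold difference, and 2 or 8 mL/kg after the procedure. No text resolves it, and it must be fixed.

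The per-kilogram conflict follows from the protocol's own figures alone. The millilitre comparisons assume the lower weight limit of each Appendix C band. The salt and sodium figures also assume 9 mg/mL and 58.44 mg of NaCl per mEq. Whether any patient received the smaller volume cannot be told from the documents. The water wording and the 177 mEq entry are smaller inconsistencies, and the conclusion does not rest on them.

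**What to change.** The sponsor should:

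1. Reconcile the Summary, sections 4.3, 4.5, 5.3, 5.5 and 7.1, and Appendix C to one intravenous regimen. At the same time, explain the 6 hours in 4.3, since 1 hour before plus 4 hours after is 5 hours unless procedure time is counted.
2. Reconcile 4.5, 5.3, 5.5 and Appendix C to one water instruction.
3. Name one table as the controlling text for both arms and have the other sections refer to it. If that table is Appendix C, also reconcile the mEq entry in its >100 kg row.
4. Check the prescribing and pharmacy instructions against that table, and judge compliance for the per-protocol analysis against it.
5. If patients have already been treated, use the intravenous quantities recorded under 5.8 and 7.2 to help establish which volume was given.

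The cost is protocol wording and a check of the working instructions. The sample size does not change. Which regimen is right is for the sponsor to settle.

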### Concomitant treatments

**Permitted:** Diuretic and hypotensive medication will be maintained, as long as there have been no changes in the previous 10 days. No changes in these medications will be allowed, except in special cases, during the 48 hours following the CE-CT. Those patients in treatment with metformin, will suspend this medication from 48 hours before to 24 hours after the administration of the contrast, and it can be replaced by the introduction or temporary increase of insulin. During the 48 hours before and 24 hours after the procedure, free water and salt intake will be allowed.

**Prohibited:** Any nephrotoxic agent will be prohibited (NSAIDs, chemotherapy or immunosuppressants, nephrotoxic antibiotics) during the 10 days before and 48 hours after the procedure.

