#### Clinical variables

The following variables will be collected between 7 days and 24 hours before contrast administration:

- General data: patient code and date of inclusion.
- Demographic data: date of birth and gender.
- Personal history: smoking, hypertension, diabetes mellitus, heart failure, dyslipidemia, ischemic heart disease, atrial fibrillation, chronic kidney disease, peripheral arterial disease, cerebrovascular disease, anemia, COPD, hypoventilation ( $\text{pCO}_2 > 50 \text{ mmHg}$ ).
- Anamnesis and physical examination: NYHA functional class orthopnea, edema in extremities, ischemic chest pain, height, weight, BMI, HR, blood pressure. Pulmonary auscultation, hepatomegaly.
- Other analytical determinations: hemoglobin, basal glycemia, glycosylated hemoglobin, oxygen saturation by pulse oximetry, BNP.
- Imaging tests: electrocardiogram.
- Concomitant medication.
- Procedure data: volume of contrast administered.

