## 8.2. Development of the study

Patients will undergo the following procedures:

Screening visit (from two months to 48 hours before the procedure): verification of inclusion and exclusion criteria. Signature of the informed consent. A laboratory blood test will be recorded within two months from the CE-CT scan. The screening visit may take place on the same day as randomization (visit 1).

Visit 1 (from two months to 48 hours before the procedure): review of inclusion and exclusion criteria. Serum creatinine, eGFR and ions will be checked. Registration of demographic and clinical data. The patient will be randomized and will receive therapeutic information to the assigned group. In the case of the oral sodium chloride arm, capsules will be provided.

Visit 2 (day of the procedure): Before the contrast administration, the investigator will ensure the patient has taken study medication. A physical examination will be performed. Furthermore, blood and urine samples will be collected for the specific analytical determinations and biomarkers. After that, contrast will be administered as well as the intravenous sodium chloride (intravenous arm). Adverse events will be reported.

Visit 3 (24 hours after contrast): The investigator will perform a physical examination, will ensure the compliance of study medication (oral NaCl arm), and will report the adverse events. Moreover, blood and urine samples will be collected.

Visit 4 (48 hours after contrast): same evaluation as visit 3, excluding compliance assessment.

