### Study Flowchart

	SCREENING (From two months to 48 hours before the procedure)	VISIT 1† (From two months to 48 hours before the procedure)	VISIT 2 (Day of the procedure; 0 hours)	VISIT 3 (24 hours after contrast)	VISIT 4 (48 hours after contrast)
Inclusion and exclusion criteria	X	X			
Informed consent	X				
Randomization		X			
Medical history		X			
Clinical variables		X	X	X	X
Contrast administration			X		
Study treatment administration		X*	X		
Evaluation of treatment compliance			X	X*	
Clinical laboratory assessments	X		X	X	X
Biomarkers			X	X	X
Adverse events evaluation		X	X	X	X

\* Patients in oral NaCl arm.

† The screening visit may take place on the same day as randomization (visit 1).

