## **10.6. Selection of subjects for analysis**

All analyses will be by intention to treat and by protocol. Since the study is a non-inferiority study, the main analysis will be per protocol.

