#### **14.2. Deviations from the protocol**

The researcher present in such circumstances will fully document the deviation and the reason in the EDC. When the deviation is related to inclusion/exclusion criteria, researchers will contact the clinical monitor by telephone to inform of the deviation.

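### Nephrotoxic-drug windows in 6.2 and 7.1 are misaligned: a patient randomised less than 7 days (or 10, depending on the 72-hour anchor) before the CT can be eligible yet already in breach

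*Combined protocol and SAP*

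**What the plan says.** Two sections of the combined protocol and SAP set rules on nephrotoxic drugs.

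- **Section 6.2 (Exclusion criteria)** rules out patients who received nephrotoxic drugs, described as "NSAIDs, aminoglycosides and/or potentially nephrotoxic chemotherapy) in the last 72 hours, or anticipation of receiving them in the following hours". It names no reference point for the 72 hours: screening, randomisation or the CT.
- **Section 7.1 (Concomitant treatments)** states: "Any nephrotoxic agent will be prohibited (NSAIDs, chemotherapy or immunosuppressants, nephrotoxic antibiotics) during the 10 days before and 48 hours after the procedure". This window is anchored to the procedure.

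Section 8.2 fixes when the criteria are applied: "Visit 1 (from two months to 48 hours before the procedure): review of inclusion and exclusion criteria". Randomisation takes place at that visit. In the Study Flowchart the row "Inclusion and exclusion criteria" is marked at screening and Visit 1 and at no later visit.

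Three other places bear on what happens to a patient in breach. Section 14.2 says: "The researcher present in such circumstances will fully document the deviation and the reason in the EDC". Section 6.4 says: "The investigator/physician may also decide to withdraw a patient from the trial if the patient does not meet the protocol standards". Section 10.6 says: "Since the study is a non-inferiority study, the main analysis will be per protocol".

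**The concern.** A restriction that starts at or after randomisation can be obeyed by an enrolled patient. The 7.1 ban reaches back 10 days before the procedure, while randomisation may be only 2 days before it. Part of the ban can therefore lie in the past when the patient is enrolled, and the eligibility screen covers only 72 hours of that past. A patient can pass every listed criterion and be a deviator on entry, with nothing left to comply with unless the CT is moved. No section tells staff to move it.

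At stake is how many avoidable deviators enter a trial that gives its per-protocol analysis priority, and whether the intended 10-day drug-free period is delivered. Section 4.1 defines the outcome condition as kidney injury without other causes and lists nephrotoxic exposure among those causes, so the protocol itself treats such exposure as relevant.

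**Working it through.** The plan gives no figure of its own to reproduce here. The check is interval arithmetic on the stated windows.

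**Inputs**
- Eligibility look-back: 72 h = 3 days, anchor not stated (6.2).
- Ban: from 10 days before to 48 h after the procedure (7.1).
- Visit 1: from two months to 48 h before the procedure (8.2).

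**Notation.** Visit 1 is *d* days before the CT (*d* ≥ 2). The most recent dose is *x* days before the CT and was taken before randomisation, so *x* ≥ *d*.

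**Conditions**
- 7.1 is breached if *x* ≤ 10.
- 6.2 is met if *x* > *d* + 3 (72 h counted from Visit 1) or if *x* > 3 (72 h counted from the procedure).
- For an agent outside the 6.2 list, if that list is exhaustive, 6.2 is always met.

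**Days on which a dose leaves the patient eligible but already in breach**
- Visit 1 anchor: max(0, 10 − (*d* + 3))
- Procedure anchor: max(0, 10 − max(*d*, 3))
- Agent named only in 7.1: max(0, 10 − *d*)

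| Visit 1, days before CT | Both lists, Visit 1 anchor | Both lists, procedure anchor | Only in 7.1 |
|---|---|---|---|
| 2 | 5 | 7 | 8 |
| 3 | 4 | 7 | 7 |
| 5 | 2 | 5 | 5 |
| 7 | 0 | 3 | 3 |
| 10 | 0 | 0 | 0 |

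The gap closes at 7 days on the Visit 1 anchor and at 10 days otherwise. Stepping through *d* hour by hour gives the same limits: for drugs on both lists the gap is open from 48 h to 167 h on the Visit 1 anchor and from 48 h to 240 h on the procedure anchor. The 240 h value arises only if a dose exactly 10 days before the CT counts as inside the ban.

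**Example.** An NSAID is taken 6 days before the CT, with Visit 1 at 2 days before it. 6 > 2 + 3 and 6 > 3, so 6.2 is met on either anchor; 6 ≤ 10, so 7.1 is breached. Clearing the window would need the CT moved by 10 − 6 = 4 days, or 5 if day 10 is counted inside.

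**Drug lists.** Section 7.1 names immunosuppressants, nephrotoxic antibiotics and chemotherapy; 6.2 names aminoglycosides and potentially nephrotoxic chemotherapy. Both name NSAIDs. The differences matter only if the 6.2 list is exhaustive.

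**Forward side.** With Visit 1 at its latest, the ban ends 48 h + 48 h = 96 h after it, and later still for an earlier Visit 1. Section 6.2 asks only about use expected over an unspecified number of hours.

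**What would catch the case.** At Visit 2, section 8.2 requires a check that study medication was taken, but names no check for prohibited drugs. Section 14.2 requires a telephone call to the monitor only for deviations from the inclusion or exclusion criteria, which this is not. The ground in 6.4 for ending participation when selection criteria were not met does not apply either, because they were met. What remains is documentation and discretionary withdrawal.

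**The case against.** The strongest reply is that the two rules do not contradict each other. A patient who satisfies the 10-day ban for a listed drug also satisfies a 72-hour rule counted from the procedure. An eligibility screen and a treatment restriction may have different windows. Section 13.1 binds investigators to the whole protocol, so a careful investigator could apply 7.1 at Visit 1 and decline the patient. The clinical variables in 5.2 include "Concomitant medication", collected between 7 days and 24 hours before contrast, so exposure may be known in time.

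Much of this stands. The rules are misaligned, not mutually exclusive. The forward limits are a loose screen set beside a conduct rule, and that is no conflict. But 7.1 is not an eligibility criterion, no text makes it one, and a medication record is not an instruction to defer or decline. Followed as written, 6.2 still admits the patient in the example.

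A reader might go further and infer two things that the documents do not support.

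- **That the comparison between arms is biased.** Exposure before randomisation cannot depend on the assigned arm, creatinine is measured on the procedure day before contrast, and intention-to-treat analyses are also run.
- **That these patients are lost from the primary analysis, with a cost in power.** No section says that a 7.1 breach removes a patient from the per-protocol set. How that set is defined is a separate and wider gap.

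**Conclusion.** The point holds as a misalignment of modest consequence. For a drug on both lists, a patient can be eligible and already in breach when Visit 1 is less than 7 days before the CT (72 hours counted from Visit 1) or less than 10 days before it (counted from the procedure). For agents named only in 7.1, the limit is about 10 days on either anchor, provided the 6.2 list is exhaustive. With randomisation 10 or more days before the CT, in a window that runs to two months, the look-back problem cannot arise at entry, apart from a dose exactly on day 10.

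The table counts calendar days. It does not measure an effect on power, error rate or the estimate. The documents give neither the distribution of Visit 1 timing nor the frequency of exposure, so the number of patients affected cannot be calculated. What is established is that the plan admits avoidable deviators to a trial whose main analysis is per protocol. That justifies a correction to the wording and no stronger claim about the validity of the result.

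**What to change.** Reword 6.2 to exclude any agent prohibited by 7.1 that was taken within 10 days before the planned CT, or is expected up to 48 hours after it. Use one drug list in both sections. Apply the criterion at Visit 1, before randomisation, against the planned CT date. Where clinically acceptable, schedule the CT so that the window is clear before the patient is randomised.

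Exposure discovered after randomisation should be recorded as a deviation, and the patient should stay in the intention-to-treat analysis. A check just before contrast should not become a route to exclusion: the trial is open-label, and by then the oral arm has already had capsules due from 48 hours before the test (Appendix C).

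The cost is amendment wording in two sections, plus probably slightly fewer eligible patients or some delayed CTs; the size of that loss cannot be derived from the documents. It has to be weighed in a trial that already expects recruitment limits: in 5.6, 8 patients a month for 30 months gives 8 × 30 = 240, against 266 required.
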